10.3.2. Definition of SAE

An SAE is defined as any untoward medical occurrence that, at any dose, meets one or more of the criteria listed:

a. Results in death

b. Is life-threatening

• The term 'life-threatening' in the definition of 'serious' refers to an event in which the participant was at risk of death at the time of the event. It does not refer to an event, which hypothetically might have caused death, if it were more severe.

c. Requires inpatient hospitalization or prolongation of existing hospitalization

- In general, hospitalization signifies that the participant has been detained (usually involving at least an overnight stay) at the hospital or emergency ward for observation and/or treatment that would not have been appropriate in the physician's office or outpatient setting. Complications that occur during hospitalization are AEs. If a complication prolongs hospitalization or fulfills any other serious criteria, the event is serious. When in doubt as to whether "hospitalization" occurred or was necessary, the AE should be considered serious.
- Hospitalization for elective treatment of a pre-existing condition that did not worsen from baseline is not considered an AE.

d. Results in persistent disability/incapacity

- The term disability means a substantial disruption of a person's ability to conduct normal life functions.
- This definition is not intended to include experiences of relatively minor medical significance such as uncomplicated headache, nausea, vomiting, diarrhea, influenza, and accidental trauma (e.g., sprained ankle) which may interfere with or prevent everyday life functions but do not constitute a substantial disruption.

e. Is a congenital anomaly/birth defect

f. Other situations:

- Medical or scientific judgment should be exercised in deciding whether SAE reporting is appropriate in other situations such as important medical events that may not be immediately life threatening or result in death or hospitalization but may jeopardize the participant or may require medical or surgical intervention to prevent one of the other outcomes listed in the above definition. These events should usually be considered serious.
- Examples of such events include invasive or malignant cancers, intensive treatment in an emergency room or at home for allergic bronchospasm, blood dyscrasias or convulsions that do not result in hospitalization, or development of drug dependency or drug abuse.

10.3.3. Recording and Follow-Up of AE and/or SAE

AE and SAE Recording

- When an AE/SAE occurs, it is the responsibility of the investigator to review all documentation (e.g., hospital
 progress notes, laboratory reports, and diagnostics reports) related to the event.
- The investigator will then record all relevant AE/SAE information in the CRF.
- It is not acceptable for the investigator to send photocopies of the participant's medical records to Medical Monitor in lieu of completion of the AE/SAE CRF page.
- There may be instances when copies of medical records for certain cases are requested by the Sponsor. In this
 case, all participant identifiers, with the exception of the participant number, will be redacted on the copies of the
 medical records before submission to the Sponsor and/or Medical Monitor.
- The investigator will attempt to establish a diagnosis of the event based on signs, symptoms, and/or other clinical information. Whenever possible, the diagnosis (not the individual signs/symptoms) will be documented as the AE/SAE.

Assessment of Intensity

The investigator will make an assessment of intensity for each AE and SAE reported during the study and assign it to 1 of the following categories:

- Mild: An event that is easily tolerated by the participant, causing minimal discomfort and not interfering with everyday activities.
- Moderate: An event that causes sufficient discomfort and interferes with normal everyday activities.
- Severe: An event that prevents normal everyday activities. An AE that is assessed as severe should not be confused with a SAE. Severe is a category utilized for rating the intensity of an event; and both AEs and SAEs can be assessed as severe.

An event is defined as 'serious' when it meets at least 1 of the predefined outcomes as described in the definition of an SAE, NOT when it is rated as severe.

Assessment of Causality

• The investigator is obligated to assess the relationship between study intervention and each occurrence of each AE/SAE.

- A "reasonable possibility" of a relationship conveys that there are facts, evidence, and/or arguments to suggest a causal relationship, rather than a relationship cannot be ruled out.
- The investigator will use clinical judgment to determine the relationship.
- Alternative causes, such as underlying disease(s), concomitant therapy, and other risk factors, as well as the temporal relationship of the event to study intervention administration will be considered and investigated.
- The investigator will also consult the Investigator's Brochure (IB) and/or Product Information, for marketed
 products, in his/her assessment.
- For each AE/SAE, the investigator must document in the medical notes that he/she has reviewed the AE/SAE and has provided an assessment of causality.
- There may be situations in which an SAE has occurred and the investigator has minimal information to include in the initial report to the Medical Monitor. However, it is very important that the investigator always make an assessment of causality for every event before the initial transmission of the SAE data to the Medical Monitor.
- The investigator may change his/her opinion of causality in light of follow-up information and send a SAE followup report with the updated causality assessment.
- The causality assessment is one of the criteria used when determining regulatory reporting requirements.

Follow-up of AEs and SAEs

- The investigator is obligated to perform or arrange for the conduct of supplemental measurements and/or evaluations as medically indicated or as requested by the Medical Monitor to elucidate the nature and/or causality of the AE or SAE as fully as possible. This may include additional laboratory tests or investigations, histopathological examinations, or consultation with other health care professionals.
- New or updated information will be recorded in the originally completed CRF.
- The investigator will submit any updated SAE data to the Medical Monitor within 24 hours of receipt of the information.

10.3.4. Reporting of SAEs

SAE Reporting to Sponsor via an Electronic Data Collection Tool

- The primary mechanism for reporting an SAE to Sponsor's Safety Risk Management department will be the electronic data collection tool.
- If the electronic system is unavailable, then the site will use the paper SAE data collection tool in order to report the event within 24 hours.
- The site will enter the SAE data into the electronic system as soon as it becomes available.
- After the study is completed at a given site, the electronic data collection tool will be taken off-line to prevent the entry of new data or changes to existing data.
- If a site receives a report of a new SAE from a study participant or receives updated data on a previously reported SAE after the electronic data collection tool has been taken off-line, then the site can report this information on a paper SAE form (see next section) or to the Medical Monitor by telephone.
- Contacts for SAE reporting can be found in the Trial Master File (TMF).

10.4. Appendix 4: Contraceptive Guidance and Collection of Pregnancy Information

Woman of Childbearing Potential (WOCBP)

A woman is considered fertile following menarche and until becoming post-menopausal unless permanently sterile (see below).

If fertility is unclear (e.g., amenorrhea in adolescents or athletes) and a menstrual cycle cannot be confirmed before first dose of study intervention, additional evaluation should be considered.

Women in the following categories are not considered WOCBP

- 1. Premenarchal
- 2. Premenopausal female with 1 of the following:
 - Documented hysterectomy
 - Documented bilateral salpingectomy
 - Documented bilateral oophorectomy

For individuals with permanent infertility due to an alternate medical cause other than the above, (e.g., mullerian agenesis, androgen insensitivity), investigator discretion should be applied to determining study entry.

Note: Documentation can come from the site personnel's: review of the participant's medical records, medical examination, or medical history interview.

- 3. Postmenopausal female
 - A postmenopausal state is defined as no menses for 12 months without an alternative medical cause.
 - A high follicle stimulating hormone (FSH) level in the postmenopausal range may be used to confirm a postmenopausal state in women not using hormonal contraception or hormonal replacement therapy (HRT). However, in the absence of 12 months of amenorrhea, confirmation with more than one FSH measurement is required.
 - Females on HRT and whose menopausal status is in doubt will be required to use one of the non-estrogen hormonal highly effective contraception methods if they wish to continue their HRT during the study. Otherwise, they must discontinue HRT to allow confirmation of postmenopausal status before study enrollment.

Contraception Guidance

Adequate contraception includes oral, injected or implanted hormonal methods of contraception, placement of an intrauterine device or system, vasectomized partner or sexual abstinence.

Collection of Pregnancy Information

Male participants with partners who become pregnant

• The investigator will attempt to collect pregnancy information on any male participant's female partner who becomes pregnant while the male participant is in this study. This

applies only to male participants who receive methotrexate, and is a reason to blind break. The participant will be withdrawn from the study due to blind break.

• After obtaining the necessary signed informed consent from the pregnant female partner directly, the investigator will record pregnancy information on the appropriate form and submit it to the Medical Monitor within 24 hours of learning of the partner's pregnancy. The female partner will also be followed to determine the outcome of the pregnancy. Information on the status of the mother and child will be forwarded to the Medical Monitor. Generally, the follow-up will be no longer than 6 to 8 weeks following the estimated delivery date. Any termination of the pregnancy will be reported regardless of fetal status (presence or absence of anomalies) or indication for the procedure.

Female Participants who become pregnant

- The investigator will collect pregnancy information on any female participant who becomes pregnant while participating in this study. The initial information will be recorded on the appropriate form and submitted to the Medical Monitor within 24 hours of learning of a participant's pregnancy. This applies only to female participants who receive MTX. The participant will be withdrawn from the study due to blind break and the teratogenic effect of methotrexate.
- The participant will be followed to determine the outcome of the pregnancy. The investigator will collect follow-up information on the participant and the neonate and the information will be forwarded to the Medical Monitor. Generally, follow-up will not be required for longer than 6 to 8 weeks beyond the estimated delivery date. Any termination of pregnancy will be reported, regardless of fetal status (presence or absence of anomalies) or indication for the procedure.
- While pregnancy itself is not considered to be an AE or SAE, any pregnancy complication or elective termination of a pregnancy for medical reasons will be reported as an AE or SAE.
- A spontaneous abortion (occurring at <22 weeks gestational age) or still birth (occurring at >22 weeks gestational age) is always considered to be an SAE and will be reported as such.
- Any post-study pregnancy related SAE considered reasonably related to the study intervention by the investigator will be reported to the Medical Monitor. While the investigator is not obligated to actively seek this information in former study participants, he or she may learn of an SAE through spontaneous reporting.

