The MERINO:2 is an extension of the MERINO trial (EudraCT number 2019-004641-33, Clincaltrials.gov number NCT04579848, REK ID 2020/187524, CTIS number 2023-510523-30-00), with an expanded observational period of 18 months after ending the MERINO trial (i.e. 30 months after staring MERINO). MERINO:2 is an investigator-initiated and open-label observational study. Participants are male and female adults with erosive hand osteoarthritis. Following the completion of the MERINO trial, participants either ended their treatment or were prescribed MTX open-label (oral or s.c. 5-25mg per week as well as folic acid 1mg daily).

Brief Summary:

The primary aim is to demonstrate the superiority of Methotrexate (MTX) over treatment as usual in slowing radiographic progression over 30 months in individuals with erosive hand osteoarthritis (OA).

OA is a leading cause of disability and affecting millions worldwide, with a significant impact on knee, hip, and hand joints. Despite its high prevalence and symptomatic burden, effective disease-modifying treatments remain elusive, with current options limited to pain management and joint replacement.

MTX, recognized for its disease-modifying effects in systemic inflammatory joint diseases, offers promising potential in OA treatment, with previous trials indicating its anti-inflammatory properties and potential for joint damage reduction. In the ongoing MERINO trial, 153 participants are randomly assigned to either MTX or a placebo. Following completion of the trial, several participants have expressed interest in MTX treatment, which is sometimes used off-label for erosive hand OA patients experiencing unmanageable pain and inflammation. As a result, some MERINO trial participants will receive MTX treatment.

In the MERINO:2 study, we will conduct a structured follow-up 18 months post-MERINO trial completion, incorporating hand radiographs and pain questionnaires. This endeavor will furnish invaluable insights into the long-term effects of MTX treatment in erosive hand OA, a gap in current knowledge, particularly regarding structural progression. This will provide valuable data on long-term effects of MTX treatment in erosive hand OA, which is not currently described in the literature, especially on structural progression.

Number of Participants:

We estimate 153 recruited participants from the MERINO trial as potential candidates for the MERINO:2 trial.

Study Arms and Duration:

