All participants recruited to the MERINO trial will be asked to provide conventional radiographs and electronic questionnaires 30 months after starting the MERINO trial. This results in four potential arms of the MERINO:2 trial, depending on the two former arms of the MERINO trial, each with a duration of 12+18=30 months:

- MTX \rightarrow MTX
- MTX \rightarrow Treatment as usual
- Placebo \rightarrow MTX
- Placebo \rightarrow Treatment as usual

Data Monitoring/Other Committee: No

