4.1. Overall Design

The MERINO:2 is an investigator-initiated and open label observational study with one-year parallel group treatment with MTX in male and female adults with erosive hand osteoarthritis.

Eligible participants are those recruited to the MERINO-trial (EudraCT number 2019-004641-33, Clincaltrials.gov number NCT04579848, REK ID 2020/187524, CTIS number 2023-510523-30-00).

After the MERINO trial, participants may either continue treatment as usual or be prescribed MTX open-label (oral or s.c. 5-25mg per week as well as folic acid 1mg daily).

Especially of interest is to compare those who first receive placebo and then treatment as usual throughout the MERINO and MERINO:2 trials with those receiving MTX throughout the whole period, as this comparison will reflect the effect of long-term treatment with MTX over 2,5 consecutive years. Further, the Placebo→MTX crossover group will complement the data from the MERINO trial on shorter MTX treatment.

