4.4. End-of-Study Definition

The end of the study is defined as the date of the last scheduled procedure shown in the schedule of activities for the last participant in the study.

A participant is considered to have completed the study if the participant has completed one-time follow-up procedure shown in the SoA 30 months after entering the original MERINO trial.

5. Study Population

All participants entering the MERINO trial (see section 4.1) will be asked if they can voluntarily can provide a 30-month conventional radiographs and an electronic questionnaire. This results in four potential arms of the MERINO:2 trial, depending on the two former arms of the MERINO trial (Table 2).

The participants must be capable of giving signed informed consent as described in Appendix 1 which includes compliance with the requirements and restrictions listed in the informed consent form (ICF) and in this protocol.

We otherwise refer to the MERINO-protocol for study population description.

Table 2. Study Arms

| MERINO | MERINO:2 |
|--------------------|----------------------------------|
| 12 months | 18 months |
| MTX 10-20mg weekly | \rightarrow Treatment as usual |
| MTX 10-20mg weekly | → MTX 7,5-20mg weekly |
| Placebo | \rightarrow Treatment as usual |
| Placebo | → MTX 7,5-20mg weekly |

6. Study Intervention(s) and Concomitant Therapy

Study interventions are all pre-specified, investigational, and non-investigational medicinal products intended to be administered to the study participants during the study conduct.

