6.4. Blinding

This is an open-label study; potential bias will be reduced by blinding the researcher who will interpret and score the radiographs.

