8.4.5. Pregnancy

• A female/male participant must be instructed to immediately inform the investigator if she/his partner becomes pregnant during the study. For details on collection of pregnancy information, see Appendix 4.

- While pregnancy itself is not considered to be an AE or SAE, any pregnancy complication or elective termination of a pregnancy for medical reasons will be reported as an AE or SAE.
- Abnormal pregnancy outcomes (eg, spontaneous abortion, fetal death, stillbirth, congenital anomalies, ectopic pregnancy) are considered SAEs and will be reported as such.
- The participant/pregnant female partner will be followed to determine the outcome of the pregnancy. The investigator will collect follow-up information on the participant/pregnant female partner and the neonate and the information will be forwarded to the sponsor.
- Any poststudy pregnancy-related SAE considered reasonably related to the study intervention by the investigator will be reported to the sponsor as described in Section 8.4.4. While the investigator is not obligated to actively seek this information in former study participants/pregnant female partner, he or she may learn of an SAE through spontaneous reporting.
- A pregnant participant should be withdrawn from the study.

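### Appendix 4 withdraws MTX-treated men with a pregnant partner for breaking a treatment blind that this open-label study does not have

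*Protocol*

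**What the plan says.** Section 10.4 (Appendix 4) asks the investigator to collect information when the partner of a male participant becomes pregnant. It adds that this "applies only to male participants who receive methotrexate, and is a reason to blind break", and then: "The participant will be withdrawn from the study due to blind break". For pregnant women on MTX the same appendix also orders withdrawal, giving both blind break and teratogenicity as reasons. Its last bullet on women covers any pregnant female participant and offers two outcomes: stopping the drug or leaving the study. Section 8.4.5 is unconditional: "A pregnant participant should be withdrawn from the study".

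On blinding, the synopsis says "MERINO:2 is an investigator-initiated and open-label observational study", and section 4.1 repeats this ("The MERINO:2 is an investigator-initiated and open label observational study"). Section 6.4 says: "This is an open-label study; potential bias will be reduced by blinding the researcher who will interpret and score the radiographs".

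Section 4.4 ties completion to a single follow-up: "A participant is considered to have completed the study if the participant has completed one-time follow-up procedure shown in the SoA 30 months" after entry to MERINO.

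**The concern.** A withdrawal rule is an operative instruction, and this one rests on an event that cannot happen in this study. The participant and the physician both know whether he takes MTX, so his partner's pregnancy reveals nothing about treatment. The rule is also mandatory, which leaves the investigator no room to keep the man in follow-up.

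What is at stake is data. MERINO:2 takes its outcomes at one time point, so withdrawal before it removes everything the study would have measured on that man. The bullets on pregnant women carry the same void reason, and one of them allows an outcome that the other texts do not.

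**Working it through.** There is no figure to reproduce. Section 9.5 says that the sample size has no statistical basis, and the point concerns wording. The check sets the sections side by side.

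**1. Is there a treatment blind in MERINO:2?** Section 6.3 has the physician and the participant decide together whether to use MTX. Sections 1.1, 4.1 and 6.4 call the study open-label. The one blinded person is the radiograph scorer, and handling a partner's pregnancy does not require telling the scorer anything. No treatment blind exists to be broken.

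**2. Could the MERINO blind be meant?** Sections 4.1 and 5 open MERINO:2 to everyone recruited to MERINO and do not require an intact blind. If a person whose MERINO allocation is known may enter, learning that allocation later is no reason to make him leave.

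**3. Is another reason given for men?** No. Teratogenicity is named only in the bullet on women. Section 2.3.1 says men should stop MTX three months before planned conception, but that concerns the drug. Section 7.2 treats stopping the drug as different from leaving the study: participants who stop are still invited to the follow-up visit.

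**4. What is lost?** In the schedule of activities, the hand radiographs and patient-reported outcomes of MERINO:2 appear only at M30. A man withdrawn earlier has no M30 Verbruggen-Veys score and no M30 questionnaire. Section 7.3 plans no imputation for loss to follow-up. His MERINO radiographs up to M12 remain, so the loss is the M30 value.

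**5. Which men are affected?** The synopsis describes the groups: "This results in four potential arms of the MERINO:2 trial, depending on the two former arms of the MERINO trial".

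- MTX then MTX, and placebo then MTX: the rule applies.
- Placebo then treatment as usual: it does not apply.
- MTX then treatment as usual: unclear, because the rule does not say when MTX must be received.

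The primary hypothesis in section 9.1 compares MTX throughout with placebo then treatment as usual. Losing a man from the placebo-then-MTX group therefore does not touch that comparison; losing one from the MTX-throughout group does.

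**6. The texts on pregnant participants.**

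| Text | Applies to | Consequence | Reason given |
|---|---|---|---|
| 8.4.5 | any pregnant participant | withdrawal | none |
| 10.4, first bullet on women | follows a sentence limited to MTX recipients | withdrawal | blind break and teratogenicity |
| 10.4, last bullet on women | any pregnant woman | stop the drug or withdrawal | none |

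Withdrawal satisfies all three rows. For a woman not on MTX, the option to stop the drug has nothing to act on, so the last row also leads to withdrawal. The one real conflict is that a woman on MTX who stops it and stays in the study complies with the last row but not with the first two.

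**The case against.** The best defence is that MERINO is described as ongoing, and the protocol does not say when each participant's allocation is disclosed. Some blind may therefore still be in force while MERINO:2 runs. That is fair, and it makes it likely that the phrase was carried over rather than chosen. It does not rescue the rule, because an intact MERINO blind is not a condition of taking part (step 2).

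A second defence is that the rule may never be triggered. Section 2.3.1 excludes persons planning a pregnancy, and section 7.3 makes the final examination voluntary in any case. This limits the importance of the point but does not make the sentence right.

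A third concerns pregnant women. Teratogenicity is a valid ground that stands without the blind-break phrase, and withdrawing pregnant participants is a permissible, cautious choice. This stands in full. A reader might infer from the table that the protocol has three conflicting pregnancy rules and cannot be followed. The documents do not support that, since withdrawal complies with every text.

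**Conclusion.** The point holds as a minor error. The only reason given for withdrawing an MTX-treated man with a pregnant partner is void, and following the rule would discard his M30 outcomes for no benefit. The blind-break reason for women is equally void, though their withdrawal has another ground.

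Each case costs one M30 assessment. The number of cases cannot be estimated, because the protocol gives no age or sex distribution, no group sizes and no expected pregnancies. That they should be rare is an assumption, supported by the exclusion of planned pregnancy.

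Two stronger readings are tempting and not supported:

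- *Bias in the primary comparison.* The rule removes only MTX-treated men, so a reader might infer bias. Nothing in the protocol shows that such losses would be more than isolated or related to progression, and some would fall outside the primary comparison.
- *Loss of safety information.* A reader might infer that pregnancy outcomes go unrecorded after withdrawal. Sections 8.4.5 and 10.4 continue that follow-up.

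**What to change.** In section 10.4:

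- Delete the blind-break wording for both men and women.
- Delete the withdrawal of men with a pregnant partner.
- Keep the collection of partner pregnancy information, and state that any decision on the man's MTX rests with the treating physician.

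Separately, align the last bullet on women in section 10.4 with section 8.4.5 and the first bullet on women, so that one rule applies to pregnant participants. Either withdrawal, or stopping MTX with continued follow-up, would be acceptable; the sponsor should choose one and state it in both sections.

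The cost is a wording amendment with no new procedure. Because it changes who is withdrawn, it needs ethics committee approval under section 10.1.1 before it takes effect, and it could go in with the next amendment.
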